6.4.3. Data Collection and Analysis Methods

Cardiac death and myocardial infarction events will be adjudicated by the CEC and the data on the CEC adjudication form will be used in the analysis.

The primary endpoint rates in the AT set for one-month clear population will be reported, as well as the two-sided 95% confidence interval. If the upper limit of the two-sided 95% confidence interval is smaller than 9.7%, the primary objective will be considered as a success.

The one-sided binomial exact test will be carried out to assess statistical significance at the 0.025 alpha level.

Revision 4.0

6.4.4. Determination of Patients/Data for Analysis

The primary analysis will be performed in the AT set for one-month clear population.

6.4.5. Missing Data Analysis

Every effort will be undertaken to minimize missing data. One-month clear AT subjects with primary endpoint events, or with CEC events on or before one year, or with any follow-up visits, assessments, or events on or after the lower window of one year follow up will be considered to have complete data for the purposes of this analysis. If outcome data are missing, to assess the potential impact of missing data, a sensitivity analysis will be conducted which will include a complete case (including only subjects whose status is known at one year), a best-case (assume missing Resolute Onyx subjects are event free at one year), a worst-case (assume missing Resolute Onyx subjects have event at one year), and a tipping point analysis if the conclusion is changed in the worst-case analysis.

6.5. Secondary Endpoints

The following secondary endpoints will be assessed:

1. Acute success (device, lesion, procedure)
2. All deaths including cardiac death
3. Major adverse cardiac event (MACE)
 - Defined as death, myocardial infarction, or clinically driven repeat target lesion revascularization by percutaneous or surgical methods
4. Composite of cardiac death and myocardial infarction
5. Target vessel failure (TVF)
 - Defined as cardiac death, target vessel myocardial infarction or clinically-driven target vessel revascularization
 - Target vessel failure will be reported when ANY of the following events occur:
 - Recurrent MI occurs in territory not clearly attributed to a vessel other than the target vessel
 - Cardiac death not clearly due to a non-target vessel endpoint
 - Target vessel revascularization is determined
6. Target lesion failure (TLF)
 - Defined as cardiac death, target vessel myocardial infarction (Q wave and non-Q wave), or clinically driven target lesion revascularization (TLR) by percutaneous or surgical methods
7. All revascularizations (TLR, TVR and non-TVR)

Revision 4.0

8. Stent thrombosis (def/prob)
9. Stroke
10. Bleeding per BARC criteria
 - BARC 3 to 5
 - BARC 2 to 5
 - All BARC

All secondary endpoints except acute success will be assessed at 1, 2 and 6 months, 1 year, and 2 years for AT set; also at 6 months, 1 year and 2 years for AT one-month clear set.

6.5.1. Data Collection and Analysis Methods

The data on the CEC adjudication form will be used in the analysis. For secondary endpoints, event rates/success rates, and 95% two-sided confidence interval will be provided. The time-sensitive nature of any response variable will be displayed by using a Kaplan-Meier plot.

The primary analysis for secondary endpoints at follow-up time points (2, 6 months, 1 and 2 years) will be performed for AT one-month clear population, except that the acute success. The secondary analysis for secondary endpoints (except acute success) at all follow-up time points (1, 2, 6 months, 1 and 2 years) will be performed based on the AT set.

6.6. Analysis of Subgroups

Subgroup analyses of the primary and secondary endpoints (AT set, AT set for one-month clear population) include the following patient characteristics.

- Acute Coronary Syndrome (ACS) vs. no ACS
Acute coronary syndrome is NSTEMI or STEMI, or unstable angina at baseline
- Diabetes vs. no diabetes
- Age (≤ 75 vs. > 75 years)
- Sex (female vs. male)
- Multi-vessel vs. Single vessel treatment
- Multi-lesion vs. Single lesion treatment
- Overlapping stent vs. none
- Off-label (Complex) vs. on-label (Simple)

For the purposes of stratification, subjects are considered “complex” if they have total occlusion or are off-label because of any of these conditions: bifurcation, saphenous vein graft (SVG), target lesion in-stent restenosis (ISR), Acute MI (≤ 72 hrs), left ventricular ejection fraction (LVEF) $< 30\%$, unprotected left main (LM), more than two vessels stented, renal insufficiency or failure (creatinine ≥ 140 $\mu\text{mol/L}$), lesion length

Revision 4.0

> 35 mm, more than one lesion per vessel, or pre-procedure thrombus. “Simple” subjects are all the subjects excluding “complex” subjects. “Simple” subjects are also on-label subjects except those have total occlusion.

- US vs. Japan (p-value from comparing US subjects to Japan subjects will be calculated)
- With staged procedure vs. without staged procedure
- OAC vs no OAC planned to continue after PCI
- Renal failure (creatinine clearance < 40 ml/min) vs. no renal failure
- Minimum stent diameter ≤ 2.5 mm vs. > 2.5 mm
- With vs without anemia or hospital admission for bleeding < 12 months
- With vs without planned major surgery during the next 12 months
- Total stent length ≤ 30 mm vs. > 30 mm
- Femoral vs. non-femoral final vascular access site
- Enrolled by age criteria only vs. not enrolled by age criteria only
- Bifurcation vs. none
- Subjects switched from DAPT to SAPT between 27 days and 35 days post procedure, to be referred to as a “medication adherent subgroup”
- Number of HBR criteria
- SAPT type after one month: aspirin vs. P2Y12 inhibitor. This only applies to one-month clear population and who actually transitioned to SAPT from DAPT.

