8.8. Staged Procedures

Treatment of all target lesions with the Resolute Onyx stent within a single PCI is encouraged, if reasonable and safe. However, when staging is required for clinical reasons, the staged procedures should be performed within 30 days from index procedures and similar to index procedure, with a Resolute Onyx stent. A staged procedure is considered a subsequent treatment of a lesion in a vessel not treated at index that is present at the time of the index procedure. Staging should be pre-specified at the time of the index procedure ~~and follow-up should be calculated from the date of index procedure~~. Cardiac enzymes should be obtained before and after the staged procedure, with the same steps as that taken for the index procedure. Lesions and vessels treated with Resolute Onyx stent at the staged procedure are considered target lesions and vessels.

In addition, staged procedures should meet the following requirements:

- Staged procedures must be pre-specified at index procedure AND completed within 30 days of index procedure to qualify as a planned staged procedure. Any additional procedure to the index procedure that does not meet these requirements may be considered as a revascularization and follow-up will be based on the timing of index procedure.
- Resolute Onyx stents should be used at both index and at staged procedures.
- Staged procedures in the target vessel(s) treated at index are NOT allowed.
- Staging should not involve a segment directly adjacent to a segment treated during the index PCI.
- Every urgent coronary reintervention before the planned staged procedure is considered an event.
- Duration of DAPT is one month following the staged procedure.
- For one-month clear analysis, the "clear" definition should be extended to one month beyond the planned staged procedure.
- Follow-up for the one month and two month time points will be calculated from the date of staged procedure; remaining follow ups will be calculated from the index procedure.

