6.1. Analysis Populations

Per the CIP, subjects will be considered enrolled into the trial after the following criteria have been met:

1. The signed and dated informed consent has been obtained
2. The patient and target vessel(s)/lesion(s) have met all of the inclusion and none of the exclusion criteria

Revision 4.0

3. The study stent is introduced into the guide catheter

Intent-to-Treat (ITT): All enrolled subjects. Time zero begins at the date of the index procedure.

As Treated (AT): All ITT subjects who received the Resolute ONYX stent only. Time zero begins at the date of the index procedure.

One-month Clear: All subjects who meet all of the following criteria:

- [REDACTED]
- [REDACTED]
- [REDACTED]

[REDACTED]

[REDACTED]

Event-free is defined as that a subject must not have myocardial infarction (MI) (excluding peri-procedural MIs), repeat coronary revascularization, stroke, stent thrombosis (ARC definite/probable), and death. [REDACTED]

[REDACTED]

As Treated and Intent-to-Treat for one-month clear are:

- As Treated Set for One-month Clear: All AT subjects who are in the one-month clear population. This is the primary cohort for the primary endpoint analysis.
- Intent-to-Treat Set for One-month Clear: All ITT subjects who are in the one-month clear population.

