6.4.2. Primary Endpoint Definition

The primary endpoint is the binary rate of the composite event rate of cardiac death, and myocardial infarction at one-year post-procedure in a one-month clear population. The numerator will be the number of one-month clear subjects who have cardiac death or myocardial infarction, on or before one-year post-procedure (365 days). The denominator will be the number of one-month clear subjects who either have CEC events on or before one year, or have latest date of all follow-up visits, assessments, or events on or after the lower window of one year follow up.

In addition, the KM event rates at 1 month, 2 months, 6 months, 1 year, and 2 years, as well as the KM plot will be provided.

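### The medication adherent subgroup is defined by a switch on days 27 to 35 but is also run in the As Treated set from day 0, which biases its event rates low, and the anchor of its window is not stated

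*SAP*

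**What the plan says.** SAP 6.6 opens with the sets in which every listed subgroup is analysed: "Subgroup analyses of the primary and secondary endpoints (AT set, AT set for one-month clear population) include the following patient characteristics". One entry is the medication adherent subgroup: "Subjects switched from DAPT to SAPT between 27 days and 35 days post procedure". No comparator is given for it, although most other entries contrast two groups.

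SAP 6.1 defines the AT set as "All ITT subjects who received the Resolute ONYX stent only. Time zero begins at the date of the index procedure". It carries no condition of being alive or event-free at one month. SAP 6.5 adds: "All secondary endpoints except acute success will be assessed at 1, 2 and 6 months, 1 year, and 2 years for AT set". The secondary endpoints include death, the composite of cardiac death and MI, and stent thrombosis.

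The other subgroup that depends on what happened to DAPT, SAPT type after one month, is restricted in 6.6: "This only applies to one-month clear population and who actually transitioned to SAPT from DAPT". The adherent subgroup has no such restriction. SAP 6.7 plans a 30-day landmark analysis in the ITT and AT sets, but exempts the adherent subgroup from it.

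For planned staged procedures, Protocol 8.8 states: "Duration of DAPT is one month following the staged procedure". Protocol 8.5 (Note 1) also starts the DAPT schedule at the staged procedure, and 8.8 allows staging up to 30 days after the index procedure. SAP 6.6 does not say which procedure starts the 27-to-35-day count.

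**The concern.** Membership is decided on days 27 to 35, while AT-set events are counted from day 0. Anyone who dies before day 27 falls outside the subgroup by construction, so mortality inside it at the 1-month assessment is almost zero whatever the effect of switching. Subjects with an early MI or stent thrombosis may also be less likely to switch on time. A table set up this way shows fewer events among those who stopped DAPT on schedule, even if the timing of the switch does nothing.

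The subgroup isolates subjects who did what the study is about. Section 6.6 is also not marked as publication-only, as 6.7 is. A reader of the AT table could take a selection artefact as support for stopping at one month.

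The second issue is the day count. If it runs from the index procedure, a staged subject who follows the Protocol can fall outside the group labelled adherent.

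**Working it through.** **Inputs from the documents.** One-year cardiac death/MI rate from day 0: 9.6%. Rate by day 30: about 3% (both SAP 5.1, Protocol 12.1.2). Classification window: days 27 to 35 (SAP 6.6). Staging: up to day 30 (Protocol 8.8).

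**Assumed, because the documents do not give them.** Share *a* of the AT set in the subgroup: 50% to 80%. Early cardiac deaths: 0.5% to 1.5% (the split of the 3% into death and MI is not stated).

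**The plan's own figure.** (9.6% − 3%) / (1 − 0.03) = 6.6 / 0.97 = 6.8%, as stated.

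**Null model.** Let *e* be the fraction of the AT set with an early event that bars entry to the subgroup. Switching has no effect on outcome, and it is unrelated to outcome among everyone else. Then:
- rate in the subgroup: A = (9.6% − e) / (1 − e)
- rate in the complement: C = (9.6% − a·A) / (1 − a)

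Worked case, e = 1.0% and a = 80%: A = 8.6 / 0.99 = 8.7%; C = (9.6 − 0.8 × 8.69) / 0.2 = 13.2% to 13.3%; ratio 0.66.

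| Barred from the subgroup | A | C, a = 60% | Ratio | C, a = 80% | Ratio |
|---|---|---|---|---|---|
| Early cardiac deaths, 0.5% | 9.1% | 10.3% | 0.89 | 11.4% | 0.80 |
| Early cardiac deaths, 1.0% | 8.7% | 11.0% | 0.79 | 13.2% | 0.66 |
| Early cardiac deaths, 1.5% | 8.2% | 11.7% | 0.70 | 15.1% | 0.54 |
| All 3% of early cardiac death/MI | 6.8% | 13.8% | 0.49 | 20.8% | 0.33 |

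In the last row, a = 50% gives 6.8% against 12.4%, a ratio of 0.55.

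Against the whole AT set the ratio is A / 9.6%, which does not depend on *a*: 9.15 / 9.6 = 0.95 at e = 0.5%, 8.22 / 9.6 = 0.86 at e = 1.5%, and 6.80 / 9.6 = 0.71 if all 3% are barred.

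**Simulation check**, again with no true effect: 1% early cardiac death, 2% early MI, and 60% or 80% of the others switching in the window. If an early MI does not change the chance of switching, the ratios are 0.80 and 0.67. If it halves that chance they are 0.64 and 0.48, and if it rules a switch out they are 0.50 and 0.36. In the 80% case with MI not affecting switching, 1-month death is 0.02% inside the subgroup and 4.7% outside.

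**Starting after classification.** Under the same null model, both groups then have about 6.8%, ratio 1.0. The one-month clear set comes close to this, because early deaths and most early events are already out. A small gap remains: the window stays open to day 35, so an event between one month and day 35 can still decide membership.

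**Staged subjects.** Suppose the count runs from the index procedure. A subject staged on day *s* who then takes 30 days of DAPT switches on day s + 30, and s + 30 ≤ 35 requires s ≤ 5. With a switch 27 days after staging, s ≤ 8. With 35 days, no staging day fits. A subject staged on day 20 switches near day 50. On the 30-day reading, staging on days 6 to 30 (25 of 30 possible days) puts a compliant subject outside the window. If the count runs from the last staged procedure, none are misplaced.

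**The case against.** Several points on the other side stand.

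- **No contrast is planned.** SAP 6.6 names one group and specifies a p-value only for US against Japan. The bias appears when the rate is read against the complement or the whole AT set. The missing comparator is itself part of the problem.
- **The main analyses are protected.** The primary endpoint is defined only in the one-month clear population, and SAP 6.5.1 makes the AT set the secondary analysis for secondary endpoints. No success rule depends on this subgroup.
- **Non-fatal early events do not bar a switch.** Protocol 8.5 (Note 2) makes longer DAPT after an early stent thrombosis optional, and a peri-procedural MI does not stop a subject from being one-month clear. Strict immortal time applies to death only. For MI and stent thrombosis it is selection of unknown strength.

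A reader might infer that the subgroup will show less than half the event rate of the rest (for example 6.8% against 16.1%, ratio 0.42, at a 70% share). That assumes every early event prevents a timely switch, which the documents do not say, so it is a ceiling.

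A reader might also infer that staged subjects are misclassified. That holds only if the days run from the index procedure, and then only for staging after about day 5 to 8. SAP 6.6 does not name the index procedure, whereas 6.7 does for its landmark. The criteria for one-month clear in SAP 6.1 are partly blacked out and may address staging. What the documents support is an anchor not stated in 6.6.

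The objection does not remove the defect: the AT-set table is called for, and deaths before day 27 are excluded from the subgroup by its definition.

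**Conclusion.** The point holds for the AT-set version of this subgroup. The direction is downward in every scenario examined. The size is uncertain: a null ratio against the complement of 0.89 to 0.70 (60% share) or 0.80 to 0.54 (80% share) if only early cardiac deaths of 0.5% to 1.5% are barred, and 0.55 to 0.33 (50% to 80% share) as the upper bound on the bias if all 3% are. These figures rest on the plan's historical rates and on assumed shares and early death rates.

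The test against the 9.7% performance goal is untouched, and the one-month clear version of the subgroup is largely sound. The stronger inference that the study's main conclusion is at risk is not supported. Separately, the window needs a stated anchor for staged subjects. This is a should-fix matter in the SAP.

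**What to change.** In SAP 6.6:

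1. Run the medication adherent subgroup only in the AT one-month clear set, as is already done for SAPT type.
2. Name the comparator: one-month clear subjects who did not switch within the window.
3. In both groups, count events only after the classification window has closed, among subjects who are event-free and in follow-up at that time.
4. State one anchor for both the window and the landmark, and reconcile it with Protocol 8.5 and 8.8 for staged subjects. The two must move together. If the window ran from the staged procedure, a subject staged on day 20 would be classified on index days 47 to 55, and a landmark fixed at index day 36 would come before classification.

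The cost is SAP wording. The few events between one month and the end of the window drop out of this one table, and the AT-set version is not produced. No data collection or sample size changes.

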6.7. Analysis for Publications for Extension of Onyx One Global RCT Study

This section describes the planned analyses for publication purpose only. Baseline demographic and clinical data from the pooled Resolute Onyx subjects will be compared to the data from the BioFreedom arm of Onyx One study for ITT, AT, and AT one-month clear sets. The cumulative analysis (from one month to 365 days post procedure) will be performed for the AT one-month clear population and the landmark analysis will be performed for ITT and AT sets on all clinical endpoints and for all subgroups defined in Section 6.6 except the US vs Japan subgroup, Medication Adherent subgroup, and SAPT type after one-month subgroup. The analysis populations for the cumulative and landmark analyses are specified in Tables 1 to 2.

Landmark analyses at 30 days for all clinical endpoints will be performed for the AT and ITT set, and will be compared to the corresponding populations in the BioFreedom arm of Onyx One Global RCT study. The Kaplan Meier method will be used to calculate event rates for events that occur between 31- and 365-days post index procedure. Subjects who died or withdrew before 30 days will be excluded from this analysis. Subjects who experienced non-terminal events (e.g., MI) before 30 days will be included from this analysis. The cumulative incidence function in the presence of a competing risk will be estimated, and comparisons between Onyx and BioFreedom arms will be made using Gray’s test.

Table 1. Analysis Populations for Pooled Cumulative Analysis

Cumulative Analysis	Planned Analysis	Analysis Population for Cumulative Analysis
All clinical endpoints, from one month to one year	Principal effective and safety table	AT one month clear

Revision 4.0

Subgroup analysis from one month to one year	Principal effective and safety table	AT one month clear
--	--------------------------------------	--------------------

Table 2. Analysis Populations for Pooled Landmark Analysis

Landmark Analysis	Planned Analysis	Analysis Population for Landmark Analysis
All clinical endpoints, from 30 days to one year	Principal effective and safety table	ITT/AT
Subgroup analysis from 30 days to one year	Principal effective and safety table	ITT/AT

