5.1. Sample Size for Primary Objective

Based on historical short DAPT studies with high-bleeding risk patient populations (LEADERS FREE, ZEUS, and SENIOR)^{1,2,3,4,5} the weighted average of cardiac death and myocardial infarction at one year was 9.6%. As disproportionately higher rates of STEMI, unstable angina, and multi-vessel disease were identified in the ZEUS study population which could have led to a higher rate of cardiac death, the ZEUS rate was revised. Similarly, the SENIOR rate contribution was derived from the published rates based on subjects with planned one-month DAPT use.

Approximately 3% of CD/MI events occurred in LEADERS FREE study at 30 days. To account for a “one-month clear” population, the weighted CD/MI rate at 12 months will be discounted by 3%, resulting in an average rate of 6.6%. In addition, to account for the 3% population that will also be removed from the denominator of the rates, the expected CD/MI rate between 30 days and one year is more accurately represented as 6.8%.

The performance goal (9.7%) incorporated a clinically acceptable margin of 2.9% to the expected rate.

In defining a “one-month clear” population, an attrition rate of 20% will be applied to account subjects who interrupted or discontinued DAPT (greater than 3 cumulative days) within the first one month of procedure, who were excluded due to events that would prohibit them from discontinuing DAPT beyond one month, who failed to transition from DAPT to single antiplatelet therapy (SAPT) one month after procedure, and who were lost to follow-up. Peri-procedural MIs will not exclude the patient from being considered as “one month clear”. For the secondary endpoints like TLF, all available biomarkers (including peri-procedural) will be forwarded to the CEC to be used towards the adjudication of events.

Assuming a one-sided alpha level of 0.025 and a true event rate of 6.8%, an effective sample size of 1360 subjects will yield a greater than 97% power to reject the null hypothesis. Assuming a 20% attrition rate, a total sample size of 1700 subjects will be needed.

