The outcomes from 700 US subjects enrolled in this study will be combined with those of 1000 subjects from the Resolute Onyx arm of the Onyx ONE Study to form the total sample size of 1700. In addition, subjects enrolled in Japan in this study who have completed their one-year follow-up at the time when the 700 US subjects have completed their one-year follow up will also be included in the primary analysis.

6. Statistical Methods

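### Minor, publication only: the SAP 6.7 landmark analysis compares pooled Onyx subjects, about 41% to 44% of them never randomised, with the RCT's BioFreedom arm by an unadjusted Gray's test

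*SAP*

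**What the plan says.** SAP 6.7 sets out comparisons of the Onyx stent with BioFreedom and limits their role: "This section describes the planned analyses for publication purpose only".

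- **Groups.** The Onyx side is pooled over the two studies: "Baseline demographic and clinical data from the pooled Resolute Onyx subjects will be compared to the data from the BioFreedom arm" of the RCT. Table 2 also describes the landmark analysis as pooled, for ITT/AT.
- **Pool.** SAP 5.1 gives its planned make-up: "The outcomes from 700 US subjects enrolled in this study will be combined with those of 1000 subjects from the Resolute Onyx arm". The arm meant is the RCT's. Japan subjects may be added.
- **Landmark analysis.** It runs from 30 days to one year, on all clinical endpoints and most of the 6.6 subgroups. The AT and ITT sets "will be compared to the corresponding populations in the BioFreedom arm of Onyx One Global RCT study". Cumulative incidence is estimated with competing risks, and "comparisons between Onyx and BioFreedom arms will be made using" Gray's test. No stratum, covariate, weight or RCT-only estimate is named.
- **Cumulative analysis.** "The cumulative analysis (from one month to 365 days post procedure) will be performed for the AT one-month clear population". The text does not say whether this analysis compares the stents, and it names no test.
- **Poolability.** SAP 6.8.1 tests for a difference between studies/regions at the 0.15 level. It covers the primary endpoint only, in AT one-month clear Onyx subjects only. A significant result leads to exploratory analysis.

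**The concern.** The Onyx and BioFreedom arms of the RCT were randomised against each other, so a difference between them can be credited to the stent. The Onyx ONE Clear subjects come from a separate single-arm study. Adding them to one side only turns a randomised contrast into one that is partly externally controlled. If event rates differ between the studies because of case mix, region, care or event ascertainment, part of that difference appears as a stent effect. A larger single-arm sample would not dilute the shift; it would raise the single-arm share.

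What is at stake is how published stent-versus-stent estimates and p-values are read. They could be taken as randomised evidence when about two fifths of one group is not randomised. No regulatory decision rule in these documents depends on them.

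**Working it through.** **Inputs from the documents**

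- Pool: 700 + 1000 = 1700 Onyx subjects (SAP 5.1). This agrees with the plan's own derivation, 1360 / (1 - 0.20) = 1700.
- Japan: up to 100 more in the single-arm study (SAP 4).
- RCT total: 2000 (Protocol 3.1). BioFreedom arm by subtraction: 2000 - 1000 = 1000 (inferred).
- Section 6.7 states no sample size, alpha or power, so the plan has no figure of its own for this contrast.

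**Assumptions**

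- No true stent effect, complete follow-up, nominal 5% two-sided level.
- Base rate 6.8%, borrowed from SAP 5.1, where it is the planning rate for the one-month clear set. The landmark set is different: "Subjects who experienced non-terminal events (e.g., MI) before 30 days will be included from this analysis". The range 5% (assumed) to 9.6% (the full-year weighted average in SAP 5.1) is therefore shown too.
- Between-study gap *d* in the single-arm subjects: 1 or 2 points, purely illustrative.

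**Step 1: share and shift.** Single-arm share *w* = 700/1700 = 0.412, or 800/1800 = 0.444 with Japan. Expected shift in the contrast = *w* × *d*:

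- *d* = 1 point: 0.41 points (0.44 with Japan)
- *d* = 2 points: 0.82 points (0.89 with Japan)

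**Step 2: rejection rate, two-proportion normal approximation.** With base rate *p*, the pooled Onyx rate is *p* + *wd*. The test standard error is √[p̄(1-p̄)(1/1700 + 1/1000)], where p̄ is the overall rate. Example for *p* = 6.8%, *d* = -2 points:

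- Pooled Onyx rate = (700 × 0.048 + 1000 × 0.068)/1700 = 0.0598; difference = -0.0082.
- Standard error 0.0097 under the null and 0.0098 under the alternative; rejection probability 0.140.

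| Base rate | *d* = -2 | *d* = -1 | *d* = +1 | *d* = +2 |
|---|---|---|---|---|
| 5.0% | 17.5% | 8.0% | 7.2% | 14.3% |
| 6.8% | 14.0% | 7.2% | 6.7% | 12.1% |
| 9.6% | 11.4% | 6.6% | 6.3% | 10.3% |

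A negative *d* means a lower rate in the single-arm study. With Japan (1000 + 800 versus 1000) at 6.8%, the 2-point figures are 15.9% (lower) and 13.4% (higher).

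**Step 3: check with Gray's test.** A simulation of 40,000 trials at 6.8%, with event times uniform over the window, gave 14.0%, 7.2%, 5.1%, 6.7% and 12.2% for *d* = -2, -1, 0, +1 and +2. This agrees with the approximation.

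**Step 4: precision of the RCT-only contrast.** Half-width = 1.96 × √[p(1-p)(1/n₁ + 1/n₂)] at *p* = 6.8%:

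- 1000 versus 1000: 2.21 points
- 1700 versus 1000: 1.97 points
- Ratio: √(0.002000/0.001588) = 1.12, whatever the base rate

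**The case against.** **No decision rests on it.** Section 6.7 has no hypothesis, alpha or success rule, and the performance-goal test uses no BioFreedom data. This stands, and it is why the point is minor. The 5% level used above is a convention, not the SAP's.

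**The gap is assumed.** No document reports a difference between the studies, and Protocol 7.1 says the study is designed to have a population similar to the RCT's. This also stands. A reader might infer that the pooled comparison is biased by some known amount; the documents do not support that. They show only how much of a difference, if there is one, would pass through.

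**Section 6.7 already compares baseline data.** Readers will see measured imbalance beside the contrast. That is a partial safeguard, but nothing carries it into the test.

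**Section 6.8.1 tests poolability.** A reader might infer that a pass at 0.15 makes the pooled contrast safe. It does not. The test covers neither the landmark sets nor most of the endpoints, and nothing in 6.8 says that its result alters 6.7. Nor would it help as a gate. With 800 + 560 Onyx versus 800 BioFreedom (80% of the planned numbers) at 6.8%, rejection among trials that pass is about 13% / 10% at a 2-point gap (single-arm rate lower / higher) and 26% / 17% at 3 points. Without the gate it is 12% / 11% and 22% / 18%.

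**The RCT has its own analysis plan.** It may report the randomised landmark comparison, and we cannot see it. The absence of an RCT-only estimate from 6.7 does not show that none will be published. It does mean that 6.7 does not commit to placing one beside the pooled result.

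**Study and region are not the same thing.** Japan subjects belong to the single-arm study but are not US subjects. With 100 of them, the single-arm study's share is 800/1800 = 44%, while its US subjects are 700/1800 = 39%. The 0.41 to 0.44 figure is for a between-study difference.

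**Conclusion.** The point holds as a low-priority improvement to a publication analysis. The landmark contrast in 6.7 mixes randomised and non-randomised Onyx subjects, names nothing to separate or adjust for them, and would carry about 0.41 to 0.44 of any between-study difference in event rates. Under the stated assumptions, a nominal 5% test at a 6.8% base rate rejects about 7% of the time with a 1-point gap and 12% to 14% with a 2-point gap. Across base rates of 5% to 9.6% the ranges are 6.3% to 8.0% and 10.3% to 17.5%.

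These figures rest on the planned pool in SAP 5.1, which was set for the performance-goal analysis; the actual landmark sets may differ. They also rest on an inferred BioFreedom arm of 1000 and on assumed gaps. That 6.7 is unadjusted is read from its silence on adjustment.

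Two stronger readings are not supported: that the primary conclusion against 9.7% is compromised, and that the cumulative one-month clear analysis certainly makes the same comparison. The latter is plausible, because the baseline comparison includes that set, but the text does not say so.

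**What to change.** In SAP 6.7:

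1. Make the RCT-only Onyx versus BioFreedom landmark estimate the lead stent comparison. ITT is the randomised set, though the landmark removes deaths and withdrawals before 30 days, so even this is not a full randomised comparison.
2. Give the pooled contrast as supportive and label it non-randomised. Adjust it for the baseline variables already tabulated, for example by propensity weighting, and name the weighted method that will accompany or replace Gray's test. Stratifying by study is not an alternative way to use the single-arm subjects: their stratum has no BioFreedom subjects and adds nothing to the stent contrast.
3. State whether the cumulative one-month clear analysis compares the stents. If it does, name the test and apply the same approach.

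**Cost.** A few sentences of SAP text and some extra analysis; no new data. The RCT-only 95% interval is about 12% wider, roughly ±2.2 against ±2.0 points at 6.8%. Adjustment deals only with measured covariates and cannot remove unmeasured study or region effects, which is why the RCT-only estimate should lead.
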